Cover page study protocol

Study Title: Application of transcranial magnetic stimulation treatment in patients with oncological neuropathic pain to evaluate effectiveness on pain and quality of life

NCT number: 05480410

Date of the document: 1/02/2022

Study protocol

The protocol will be structured according to the national institute of health, the statements described by the clinical trial database and the SPIRIT declaration, which include detailed study description and design, intervention, outcome measures and individual participant data and results sharing statement.

10 patients will receive 20 sessions of transcranial magnetic stimulation using the MagVenture Mag Pro R20 device. These sessions will be conducted daily from Monday to Friday, lasting 20 minutes each, at an intensity of 81% with a motor threshold of 90 A/ns.

A pre-post design without a control group will be used to evaluate 2 elements: pain and quality of life.

The evaluation moments will be as follows:

- Pretest: Quality of life and pain will be assessed using the Visual Analog Scale (VAS) and the Brief Pain Inventory (BPI).

- Each session: Pain will be assessed using the VAS.

- Each week: Pain will be assessed using the BPI.

- Immediate Posttest: Quality of life and pain will be assessed using both scales.

- Posttest at 1 month and 3 months: Quality of life and pain will be assessed using both scales.

The patients will meet the following inclusion criteria: female or males aged over 18 and under 75 years, any stage of cancer, chemotherapeutic treatment consisting of taxanos or oxaliplatin, neuropathic pain with a minimum grade 2 severity based on the National Cancer Institute Common Terminology Criteria for Adverse Events scale (NCI-CTCAE, version 5.0), and a mean 2 score or above in a visual analogue scale (VAS) of pain. We will exclude patients with any psychiatric disorder including major depression; history of seizure, epilepsy, stroke and intracranial metallic devices. Patients should agree to avoid any extra use of medication or to make any changes to their pharmacological plan during the trial.

The aim of collecting these variables is to gather data and conduct statistical analysis to evaluate the effectiveness of transcranial magnetic stimulation on pain and quality of life in patients with neuropathic pain secondary to oncological treatment.

TEST 1: Pain

This symptom will be evaluated using the Visual Analog Scale for pain and the Brief Pain Inventory (BPI), questionnaires that have been previously used in oncology populations (Goto et al., 2020; Khedr et al., 2015).

The Visual Analog Scale is rated from 0 to 10, where 0 indicates no pain and 10 represents the maximum pain.

The Brief Pain Inventory allows patients to rate the severity of their pain and the extent to which their pain interferes with their functionality.

An average is calculated for the elements that compose the pain severity category (worst pain, least pain, average pain, and current pain) and the elements that compose the pain interference category in functionality (interference in mood, walking, working, social interactions, sleeping, and enjoyment of life). Higher averages indicate worse patient condition.

Test 2: Quality of Life

Quality of life will be assessed using the Functional Assessment of Cancer Therapy FACT-GOG-NTX 13 scale, which has been psychometrically analyzed and validated in oncology populations (Cheng et al., 2020).

This scale includes 5 categories:

- Physical Well-being
- Social Well-being
- Emotional Well-being
- Functional Well-being
- Neurotoxicity

For scoring the scale, the ratings of these categories are summed, a higher total score means a better quality of life.

Determination of resting motor threshold

The target stimulation will be the primary motor cortex in its subdivision representing the hand; for this process, a basic trained operator identify the 'omega-shape' sulcus defining the Rolandic sulcus. Other authors have reported this specific hot spot target including the expert consensus established by a group of European experts, they described a Level A recommendation for the use of M1 as stimulation site for analgesic effect. Then the accurate position of the target will be adjusted according to the amplitude of the motor response on the contralateral hand, which a basic rTMS-trained physiotherapist will confirmed. This target has been shown in different investigations, to have greater specificity and effectiveness in the treatment of neuropathic pain. Once the target will be identified, it should be marked on a cap for the following sessions. A physiotherapist will be present weekly for assessment and to supervise patients' responses to treatment.

The occurrence of adverse events will be noted throughout the study period.

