Statistical Analysis Plan (SAP)

Study Title: Effectiveness of rTMS on Pain and Quality of Life in Patients With Cancer Neuropathic Pain

NCT Number: NCT05480410 **Version Date**: 5/06/2024

1. Objectives of the Statistical Analysis

The primary objective of the statistical analysis is to assess the effectiveness of transcranial magnetic stimulation (TMS) in reducing oncological neuropathic pain and improving quality of life in patients with cancer. This includes analyzing changes in Visual Analogue Scale (VAS), Brief Pain Inventory (BPI), and quality of life indicators (FACT-G and NTX subscales).

2. General Considerations

- All analyses will be conducted using IBM SPSS Statistics software (version specified in final results).
- A p-value < 0.05 will be considered statistically significant.
- No data imputation will be performed; all analyses will be based on observed values (complete case analysis).
- Assumptions required for each test (e.g., normality) will be tested and reported.

3. Descriptive Analyses

- Continuous variables (e.g., age, VAS scores, BPI scores) will be described using means, standard deviations, medians, ranges, and percentiles, depending on the distribution of the data.
- Categorical variables (e.g., sex) will be reported as frequencies and percentages.

4. Assessment of Normality

- The normality of continuous outcome variables will be tested using the **Shapiro-Wilk** test.
- If variables are not normally distributed, non-parametric methods will be used for inferential comparisons.

5. Inferential Analyses

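### Eligibility accepts any cancer stage but does not ask whether the patient is expected to complete about 17 weeks, so illness-related late losses may bias the 1- and 3-month results

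*Protocol*

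**What the plan says.** The Protocol plans a small single-arm study: "10 patients will receive 20 sessions of transcranial magnetic stimulation", and "A pre-post design without a control group will be used". The treatment phase is intensive: "These sessions will be conducted daily from Monday to Friday, lasting 20 minutes each". Follow-up continues after it: "Posttest at 1 month and 3 months: Quality of life and pain will be assessed using both scales".

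On disease extent, the inclusion criteria accept "any stage of cancer, chemotherapeutic treatment consisting of taxanos or oxaliplatin". On age they accept "female or males aged over 18 and under 75 years". The exclusions are neurological and psychiatric: "We will exclude patients with any psychiatric disorder including major depression; history of seizure, epilepsy, stroke and intracranial metallic devices". Patients must also agree not to alter their medication during the trial. Neither document has a criterion on performance status, expected survival, disease stability or ability to attend. Neither has a dropout allowance or a replacement rule.

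SAP section 2 sets the missing-data rule: "No data imputation will be performed; all analyses will be based on observed values (complete case analysis". SAP section 5.1 compares baseline with later time points by Wilcoxon signed-rank test, or by paired t-test where the data look normal. Section 5.2 adds repeated measures ANOVA. Section 6 mentions linear mixed models only as a possibility, if the sample size permits, and for adjusting for confounders. The SAP has no rule for death or progression and no sensitivity analysis for missing data.

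**The concern.** The 1- and 3-month assessments are the trial's only evidence on whether any benefit lasts. Under the written criteria, a patient with advanced disease can enter without anyone having judged whether those assessments are likely to be reached. Loss through progression, hospital admission or death is plausibly linked to quality of life and may be linked to pain.

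Three features of the plan would turn such loss into a biased result:

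- Complete-case analysis compares only the patients who remain.
- Without a control arm, no comparison can show that an apparent improvement came from who stayed.
- Repeated measures ANOVA, as usually run, drops a patient who misses any included time point. If the 3-month visit is in the model, one late loss also removes that patient's earlier data.

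With 10 patients, each loss is a tenth of the sample.

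**Working it through.** The plan states no power, SD, effect size or dropout rate, so there is no figure of its own to reproduce. The loss rates and gaps below are assumptions chosen to show a range.

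**1. Length of the schedule.** Inputs from the Protocol: 20 sessions, 5 per week, last posttest at 3 months. Treatment is 20/5 = 4.0 weeks. Three months is 3 × 365.25/12/7 = 13.0 weeks. The total is 17.0 weeks, or 4 + 12 = 16 if a month is taken as 4 weeks. This assumes that the months run from the end of treatment. Attendance is daily only in the first 4 weeks; two follow-up assessments come after that.

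**2. Chance of losing patients.** With 10 patients and an assumed independent loss rate d, P(at least one lost) = 1 − (1 − d)^10.

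| Assumed loss | At least 1 lost | 3 or more lost | Expected completers |
|---|---|---|---|
| 5% | 40% | 1% | 9.5 |
| 10% | 65% | 7% | 9 |
| 20% | 89% | 32% | 8 |
| 30% | 97% | 62% | 7 |

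**3. Precision.** The 95% half-width for a mean change, in units of the SD of the change, is t(0.975, n−1)/√n. The power column is for a two-sided paired t-test at 0.05, from the noncentral t distribution, with an assumed standardised change of 1.0.

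| n | Half-width (SD) | Relative to n = 10 | Power |
|---|---|---|---|
| 10 | 0.715 | – | 80% |
| 8 | 0.836 | +17% | 68% |
| 6 | 1.049 | +47% | 51% |

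These rows show what loss from any cause would cost. They do not show what the missing criterion alone costs.

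**4. Bias.** The completers' mean differs from the mean of all patients by (share lost) × (gap between lost and retained patients). If 2 of 10 are lost and their change would have been 2 VAS points worse than the others', the bias is 0.2 × 2 = 0.4 points toward benefit. With 3 lost and a 3-point gap it is 0.3 × 3 = 0.9. Put another way, suppose the true mean change is 0 and each of k lost patients would have worsened by 2 points. The completers then show −2k/(10 − k): −0.50 for k = 2 and −0.86 for k = 3.

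**5. Significance with few pairs.** The smallest exact two-sided Wilcoxon p is 2/2^n: 0.031 with 6 pairs and 0.0625 with 5. The SAP does not name the exact version. With 5 differences of the same sign, the normal approximation gives z = 7.5/√13.75 = 2.02, p = 0.043. A paired t-test on 5 pairs can also fall below 0.05.

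**The case against.** The strongest reply is that nothing in the documents shows that patients will be lost. They give no stage mix, survival or dropout figure. The calculations price attrition in general, and the part that an eligibility criterion would prevent is unknown. This stands: the losses are a possibility that the criteria leave open.

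Accepting every stage may also be deliberate in a study that SAP section 7 calls exploratory. Excluding frail patients does not recover their data; it changes the population to which the result applies. A reader might infer that eligibility is the only place for a remedy. The documents do not support that, because reporting and analysis can address part of the problem without narrowing entry. They cannot do all of it: modelling informative loss in about 10 patients rests largely on assumptions that cannot be tested.

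The burden can be overstated too. Daily attendance lasts 4 weeks. The Protocol does not say that the 1- and 3-month assessments are in person, and the instruments are patient ratings. The age limit, the stroke exclusion and the agreement to keep medication unchanged act as partial filters, and daily sessions may deter the frailest patients. None of these is a written judgement that the patient is expected to reach 3 months.

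Finally, the target is neuropathic pain caused by treatment, so the documents do not establish that progression would worsen VAS. The link to quality of life is more plausible.

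**Conclusion.** The gap is real and modest. The criteria allow patients with advanced disease to enter without any recorded expectation that they will be assessable about 17 weeks later, and the SAP would analyse whoever remains. If illness-related losses occur, the 1- and 3-month results would lean toward improvement and lose precision. Losing 2 of 10 patients, for example, widens the interval by 17% and, with an assumed 2-point gap, shifts mean VAS change by 0.4. These sizes rest on assumed losses and gaps. Comparisons during treatment and at the immediate posttest, which include the Day 5 and Day 10 examples in SAP section 5.1, are less exposed.

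Two stronger readings should be avoided. A reader might infer that patients entered under these criteria are unlikely to finish; no figure in the documents supports that for the sample as a whole. A reader might also infer that significance becomes unattainable with 5 completers. That holds only for the exact Wilcoxon test; the SAP also allows paired t-tests and does not exclude the asymptotic Wilcoxon.

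**What to change.** Add one sentence to the Protocol's inclusion criteria: the investigator expects the patient to be able to complete the four weeks of sessions and to be alive and assessable through the 3-month posttest. Record that judgement at screening together with its basis. The basis, including any performance-status limit, is for the investigators to choose. Keep the acceptance of all stages otherwise.

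In the SAP, require the number of late losses and the reason for each to be reported, and use all observed data, for example through a mixed model, so that a patient who misses one time point is not dropped. A mixed model does not remove bias from informative loss, so the reasons for loss still need to be read alongside the late results.

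The cost is small: one sentence, one screening entry and a change of analysis method. The downside is a somewhat smaller pool, and results that apply to patients expected to complete the schedule. If enrolment has already closed, which the documents do not say, only the reporting and analysis changes remain available.

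### The eligibility criteria admit every cancer stage and exclude on seizure and intracranial grounds, but say nothing about known brain metastases or other intracranial tumour

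*Protocol*

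**What the plan says.** All eligibility criteria stand in one paragraph of the Protocol, under the heading Study protocol.

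- **Disease extent.** The only statement is "any stage of cancer". Neither the site of metastases nor the brain is mentioned.
- **Other inclusion limits.** These are age, treatment and symptoms: "chemotherapeutic treatment consisting of taxanos or oxaliplatin, neuropathic pain with a minimum grade 2 severity", plus a minimum VAS score. None concerns the brain.
- **Exclusions, in full.** Psychiatric disorder (major depression is named as an instance) and "history of seizure, epilepsy, stroke and intracranial metallic devices".
- **Medication.** Patients agree to keep their drug treatment unchanged during the trial.

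Under Determination of resting motor threshold, the Protocol sets the site of stimulation: "The target stimulation will be the primary motor cortex in its subdivision representing the hand". To find it, "a basic trained operator identify the 'omega-shape' sulcus defining the Rolandic sulcus", and the position is then adjusted by the motor response of the opposite hand. On safety, the same section says "The occurrence of adverse events will be noted throughout the study period".

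The SAP has no text on eligibility, intracranial disease or safety analysis.

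**The concern.** Three of the listed exclusions (seizure, epilepsy, stroke) and the fourth (intracranial metal) serve a recognisable purpose. They keep out patients in whom stimulating the cortex might provoke a seizure, or whose intracranial condition makes stimulation inadvisable. The list would suit a general chronic-pain population. This trial recruits cancer patients at every stage, so metastatic disease is expected among those screened, and a tumour inside the skull is an obvious further route to the same hazard. That cancer-specific item is the one not listed.

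What is at stake is patient safety. Someone applying the criteria exactly as written would enrol a patient whom the Protocol's own reasoning points towards screening out. An investigator might decline to enrol such a patient on judgement, but no criterion provides for that.

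**Working it through.** The documents state no figure on this point, so there is nothing to reproduce. The check has three parts.

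**1. Apply the written criteria to a test case.** Take a patient with stage IV cancer and a known brain metastasis, aged within the limits and treated with a taxane. The patient has neuropathic pain of grade 2 and a VAS of 2 or more, and agrees to keep medication unchanged. The patient has no psychiatric disorder, seizure, epilepsy, stroke or intracranial metal.

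| Criterion | Result |
|---|---|
| Age | met |
| Stage | met (any) |
| Chemotherapy | met |
| Pain grade and VAS | met |
| Medication agreement | met |
| Psychiatric exclusion | does not apply |
| Seizure, epilepsy or stroke exclusion | does not apply |
| Intracranial metal exclusion | does not apply |

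Every inclusion criterion is met and no exclusion applies, so the patient is eligible. If the tumour had already caused a seizure, epilepsy or a stroke, the patient would be excluded. The gap is therefore limited to patients with an intracranial tumour and none of the listed conditions.

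**2. Look for a later step that closes the gap.**

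- *Targeting.* Identifying a sulcus may imply a brain image, but no imaging method is named and no finding leads to exclusion.
- *Supervision.* A physiotherapist attends weekly to assess patients and supervise their responses, which happens after enrolment.
- *Adverse events.* These are recorded once they have occurred.
- *SAP.* Nothing in Sections 1 to 9 bears on eligibility.

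None of these stops the test patient from being enrolled.

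**3. Illustrate the chance of enrolling such a patient.**

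- Number treated: n = 10 (Protocol, Study protocol).
- Rate p of known or unknown brain metastases among eligible patients: not given in the documents. Assumed range 2% to 10%.
- Formula, taking patients as independent with the same rate: P(at least one) = 1 − (1 − p)^n.
- p = 0.02: 1 − 0.98^10 = 1 − 0.817 = 0.183, about 18%.
- p = 0.10: 1 − 0.90^10 = 1 − 0.349 = 0.651, about 65%.

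The width of this range comes entirely from the assumed rate. The finding in part 1 does not depend on it.

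**The case against.** The strongest reply is that inclusion and exclusion criteria apply jointly. The stage criterion sets the breadth of disease and the exclusions then narrow it, so the two do not conflict. This stands. A reader might infer that the Protocol contradicts itself; it does not. It leaves one item unaddressed.

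Four further points limit what can be claimed.

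- **Scope of the exclusions.** It is tempting to say that they cover only past events and metal. Epilepsy is a standing diagnosis, and a tumour that has already declared itself through a seizure or stroke is caught.
- **Targeting.** A reader might infer that a lesion near the landmark would make that patient's pain result meaningless. The documents do not support this, because the final position is set by the hand motor response, which a trained physiotherapist confirms.
- **Safety result.** A reader might infer that a single seizure in 10 patients would swamp the safety findings. The SAP defines no safety endpoint or safety analysis, and the documents give no seizure risk with or without a lesion, so that consequence cannot be sized.
- **The 18% to 65%.** Nothing in the documents anchors the 2% to 10%. The assumed rate also makes no separate allowance for patients removed by the seizure, epilepsy and stroke exclusions or by the required pain grade.

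It could also be said that this is only missing detail, left to clinical judgement. That does not stand. The written criteria give a definite answer for the test patient, and that answer is eligible.

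**Conclusion.** The concern holds as an omission. Neither document addresses known brain metastases or another intracranial tumour. A patient with one, and with none of the listed conditions, qualifies for 20 motor-cortex sessions, although the Protocol's exclusions treat seizure liability and intracranial abnormality as reasons not to stimulate. This conclusion rests on the wording of the criteria alone.

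Its size is uncertain. Under an assumed rate of 2% to 10%, the chance that at least one of 10 patients is affected is 18% to 65%. That describes who might be enrolled; it is not a risk of seizure or of a changed pain result. The documents do not show that such a patient was or will be enrolled, nor that the planned analyses of VAS, BPI or quality of life are affected.

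**What to change.** Reconcile the stage criterion with the seizure and intracranial exclusions, so that the eligibility criteria deal explicitly with known intracranial tumour or metastases on the same safety basis. State how this is established at screening, using the oncology record that already exists. The exact clinical rule is for the sponsor and investigators to set.

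The check should not rely on a brain image taken for targeting, since the Protocol names none. A record check finds only lesions already known; undiagnosed ones would remain, and the Protocol should say so.

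If enrolment is already complete, the final report should state whether any participant had a known intracranial lesion.

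The cost is one clause and a review of existing records for each candidate. The downside is that possibly a few advanced-stage patients are not enrolled. The statistical analysis does not change.

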5.2. Repeated Measures Analysis

- **Repeated measures ANOVA** will be conducted to evaluate the impact of the intervention over multiple time points for continuous outcome variables such as VAS, FACT-G, and TOI.
- When the sphericity assumption is violated (tested via **Mauchly's test**), Greenhouse-Geisser or Huynh-Feldt corrections will be applied.
- Effect sizes (partial eta squared) and observed power will be reported for all significant outcomes.

6. Multivariable Analysis

• If sample size allows, analysis of covariance (ANCOVA) or linear mixed models may be considered to adjust for potential confounders such as age, sex, and baseline pain level.

7. Handling of Multiple Comparisons

• Due to the exploratory nature of the study and small sample size, no formal adjustment for multiple comparisons will be applied. However, results will be interpreted with caution, and this limitation will be noted in the final report.

8. Subgroup Analyses

• No pre-specified subgroup analyses are planned due to limited sample size.

9. Deviations from Planned Analysis

• Any deviations from this pre-specified plan will be documented and justified in the final study report.

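### The only implant exclusion is intracranial metal, so under the written criteria a patient with another implanted metallic or electronic device may be given 20 magnetic stimulation sessions

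*Protocol*

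**What the plan says.** Eligibility is set out in one paragraph of the protocol, under the heading Study protocol. The exclusions are given in a single sentence, which names psychiatric illness, with major depression as an example, and then "history of seizure, epilepsy, stroke and intracranial metallic devices". The inclusion criteria begin "The patients will meet the following inclusion criteria: female or males aged over 18 and under 75 years, any stage of cancer" and go on to chemotherapy type, neuropathic pain grade and a minimum pain score. None of them mentions implants.

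The exposure is stated near the start of the same section: "10 patients will receive 20 sessions of transcranial magnetic stimulation using the MagVenture Mag Pro R20 device". The section on determining the motor threshold places the target over the hand area of the primary motor cortex.

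The remaining safety text is at the end of the protocol. A physiotherapist attends weekly to assess patients and supervise their responses, and "The occurrence of adverse events will be noted throughout the study period". The SAP has no section on safety or eligibility.

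**The concern.** A trial of magnetic stimulation that excludes intracranial metallic devices appears to accept that an implant exposed to the pulses can be a reason not to treat. That reason is inferred, because the protocol gives none. The criterion is nevertheless limited in two ways: by location (inside the cranium) and by material (metallic). It says nothing of implants in the head or neck outside the cranium, and nothing of electronic function anywhere in the body.

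Eligibility screening is the only step in the documents that could keep an unsuitable implant carrier away from the stimulator. If its wording is too narrow, a screener who follows the protocol exactly may enrol such a patient, and no protocol deviation would be recorded.

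**Working it through.** There is no figure in the plan to reproduce. The check is a reading of the text, taking each place where an implant carrier could be stopped.

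1. **Exclusion criteria.** The complete list is psychiatric disorder, seizure, epilepsy, stroke and intracranial metallic devices. The sentence is visible in full, with no sign of redaction or lost text. Only the last item concerns an implant. A device clearly outside the cranium does not meet it.
2. **Inclusion criteria.** Age, cancer stage, chemotherapy, pain grade and pain score. A patient with an implant can satisfy all of them.
3. **General safety items.** Neither document has an exclusion for contraindications to magnetic stimulation, a safety screening form, or an instruction to follow the stimulator's labelling. The only other device named is the stimulator itself.
4. **Co-treatment rule.** "Patients should agree to avoid any extra use of medication or to make any changes to their pharmacological plan during the trial". This limits drug changes during the trial. It does not screen on what a patient already has implanted.
5. **Monitoring.** Recording adverse events and weekly supervision both take place after exposure has begun. They document a problem and do not prevent it.
6. **SAP.** It describes analyses only and cannot affect who is treated.

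Taken together, a patient with an implanted electronic device outside the cranium, who otherwise qualifies, fails no inclusion criterion and meets no exclusion criterion. The planned exposure for that patient is 20 sessions at 5 per week, so 20 / 5 = 4 weeks.

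Some devices are borderline. A cochlear implant could be read as inside or outside the criterion, and two screeners might decide differently. In that case the defect is ambiguity and not a clear omission.

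**The case against.** The strongest reply is that the documents do not show a hazard. No text says that any particular implant is endangered by stimulation over the hand motor cortex, and the sponsor may have meant to limit the criterion to metal near the coil. This stands in part. It rules out any claim that a named device is unsafe here, and it means the content of a wider exclusion must come from the labelling and the sponsor's medical lead. It does not remove the gap: if the limit is deliberate, the protocol does not say so, and it points to no other safeguard.

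A second reply is that the site may already use a local checklist or the manufacturer's instructions. That is possible and cannot be excluded from the documents. The point is therefore confined to what the written criteria allow.

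A third is timing. The protocol is dated 2022 and the SAP 2024, and neither states enrolment status. If recruitment is over, a change to the criteria protects nobody already treated.

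A reader might also infer a bias problem: an implanted pain device could be re-programmed during the trial, and with "A pre-post design without a control group will be used to evaluate 2 elements: pain and quality of life" the resulting change would be credited to the stimulation. The documents do not support this as an argument for the present point. A change in the drug given by an implanted pump is a change to the pharmacological plan and is already restricted. A device whose settings stay the same before and after does not by itself create a pre-post difference. What remains is an electrical pain stimulator that is re-set between assessments, and the documents give no basis for judging how often that would happen. Excluding implant carriers would also leave every other non-drug pain treatment unrestricted, so it would not be a remedy for that problem. The examples of adjustment variables in SAP section 6 ("adjust for potential confounders such as age, sex, and baseline pain level") do not bear on the eligibility gap either way.

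**Conclusion.** The point holds as a patient-safety gap in the written criteria. The sole implant exclusion does not clearly reach metallic or electronic implants in the head or neck outside the cranium, or electronic implants elsewhere, and no other text screens for them. It rests on reading the criteria as the complete screening rule, which is how they are presented.

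The size cannot be stated. The documents give no frequency of implants among eligible patients and no level of risk for any device, so a probability of enrolling such a patient, or of harm, would rest entirely on outside assumptions. A reader might go further and infer that such patients will in fact be treated, or that specific devices are known to be at risk. The documents support neither inference. The point is still worth acting on because the correction is small and it concerns the only written step that stands before exposure.

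**What to change.** Extend the exclusion from intracranial metal to implanted metallic or electronic devices that the stimulator's labelling contraindicates, wherever they are in the body. The sponsor's medical lead should set the exact list against that labelling, including how borderline devices such as cochlear implants are classed. Add one question about implants at screening and record the answer. If the site already makes such a check, cite it in the protocol.

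If enrolment has finished, the report should instead state what implant screening was applied and whether any treated patient had an implanted device.

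The cost is one line in the exclusion criteria and one screening question. The downside is that a few otherwise eligible patients may not be enrolled, which matters somewhat in a trial of 10. No change to the SAP is needed.
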